### 3.3 Exploratory endpoints

- The quantity of CD3+ T-cells in peripheral blood and in tumor biopsies at each timepoint (baseline, cycle 3, and off-study).
- The expression category in tumor tissue (none (0%), low (<5%), intermediate (5-50%), or high (>50%) of PD-1, PD-L1, PD-L2, CTLA-4, TIM-3, LAG-3 at each timepoint (baseline, cycle 3, and off-study).
- The following T cell subsets will be studied in peripheral blood and tumor tissue: (CD4, CD8, T-reg, CTLA4, TIM3, LAG3, memory, naïve, PD-1, Ki67). For each subset, the absolute change in the relevant marker(s) value will be calculated:
  - Cycle 3 marker value minus Baseline marker value
  - Off-study marker value minus Cycle 3 marker value
  - Off-study marker value minus Baseline marker value

Evaluable criteria:

Eligible subjects who receive at least one cycle of each study drug, and successfully undergo at least one post-treatment core biopsy and blood draw.

- Utilizing each of the alternative (non-RECIST) radiological criteria we will categorize clinical benefit status (CR/PR/SD vs PD). CT and/or MRI with dynamic contrast enhanced sequences will be collected throughout the study at every disease evaluation and analyzed using Choi criteria, MRI volumetrics, and immune-related response criteria. PET/CT will be obtained at baseline, Cycle 3, and off-study and tumor response determined by PERCIST 1.0.

Evaluable criteria:

Eligible patients who receive at least one cycle of each study drug and undergo at least one post-treatment radiographic imaging study.

- The quantity of circulating tumor cells (CTCs) in peripheral blood will be measured at three timepoints: 1. Baseline, 2. Cycle 3, and 3. Off-study.

Evaluable criteria:

Eligible patients who receive at least one cycle of each study drug and undergo at least one post-treatment blood sampling.

- RNA expression of a panel of angiogenesis and immune related genes in tumor biopsies and peripheral blood samples. Expression profiles will be obtained at baseline and at Cycle 3 Day 1 on treatment.

Evaluable criteria: Eligible patients who receive at least one cycle of study drug and undergo at least one post-treated radiographic imaging study.

- T cell clonality indices in tumor and peripheral blood obtained at baseline and at Cycle 3 Day 1.

Evaluable criteria: Eligible patients who receive at least one cycle of study drug and undergo at least one post-treated radiographic imaging study.

- Plasma angiogenic activity at baseline and the ratio between on-treatment (either Cycle 1 Day 8 or Cycle 3 Day 1) and baseline.

Evaluable criteria: Eligible patients who receive at least one cycle of study drug and undergo at least one post-treated radiographic imaging study.

#### 4.0 SUBJECT RECRUITMENT & SCREENING

Subjects will be recruited at Sylvester Comprehensive Cancer Center via clinical practice offices. Both men and women of all races and ethnic groups are eligible for this trial. Informed consent documents will be translated and available in English and Spanish.

The intervention in the study holds out a prospect of direct benefit that is important to the health or well-being of minors and is available only in the context of the research. Thus minors 16 years of age and older are included in the subject population.

#### 5.0 PATIENT SELECTION

##### 5.1 Inclusion Criteria

1. Patients must have histologically confirmed sarcoma with pathology review required for any outside samples.
2. The following histologies may be enrolled without prior treatment:

- a. alveolar soft part sarcoma, (NOTE: expansion only permits patients with ASPS)
  - b. clear cell sarcoma,
  - c. epithelioid hemangioendothelioma, and
  - d. chordoma.
3. The following histologies may be enrolled ONLY if refractory to anthracycline-based chemotherapy or if the patient refuses to undergo standard of care treatment:
    - a. synovial sarcoma,
    - b. rhabdomyosarcoma,
    - c. malignant peripheral nerve sheath tumors,
    - d. dedifferentiated, pleomorphic or myxoid/round cell liposarcoma,
    - e. leiomyosarcoma,
    - f. malignant phylloides tumor,
    - g. high grade undifferentiated pleomorphic sarcomas (HGUPS/MFH),
    - h. angiosarcoma,
    - i. spindle cell sarcoma NOS
    - j. malignant myoepithelioma.
  4. The following histologies may be enrolled ONLY if refractory to at least one line of chemotherapy or if the patient refuses to undergo standard of care treatment:
    - a. solitary fibrous tumor/hemangiopericytoma.
  5. The following histologies may be enrolled ONLY if refractory to at least first-line targeted therapy or if the patient refuses to undergo standard of care treatment:
    - a. gastrointestinal stromal tumors,
    - b. extraskeletal myxoid chondrosarcoma,
    - c. PEComa.
  6. Primary tumors of bone including Ewing’s sarcoma, osteosarcoma, and dedifferentiated chondrosarcoma may only be enrolled if there are measurable target lesions occurring in soft tissue and they are refractory to standard of care anthracycline-based chemotherapy.
  7. Any other histology or standard of care treatment not specifically addressed will be reviewed by the principal investigator and pathologist for final determination of eligibility.
  8. Measurable disease as defined by RECIST v1.1 (provided in Section 14.0).
  9. Radiographic progression as defined by RECIST v1.1, based on comparison between two radiographic studies no greater than 6 months apart.
  10. Inability to undergo complete resection of the disease by surgery.
  11. Adequate organ function as defined in Table 2 (below):

System	Laboratory Value
Hematological	
Absolute neutrophil count (ANC)	$\geq 1,000$ /mcL

Platelets	≥75,000 / mcL
Hemoglobin	≥8 g/dL without transfusion or EPO dependency (within 7 days of assessment)
Renal	
Serum creatinine OR Measured or calculated a creatinine clearance (GFR can also be used in place of creatinine or CrCl)	≤1.5 X upper limit of normal (ULN) OR  ≥60 mL/min for subject with creatinine levels > 1.5 X institutional ULN
Hepatic	
Serum total bilirubin	≤ 1.5 X ULN OR Direct bilirubin ≤ ULN for subjects with total bilirubin levels > 1.5 ULN
AST (SGOT) and ALT (SGPT)	≤ 2.5 X ULN OR ≤ 5 X ULN for subjects with liver metastases
Albumin	≥2.5 mg/dL
Coagulation	
International Normalized Ratio (INR) or Prothrombin Time (PT)	≤1.5 X ULN unless subject is receiving anticoagulant therapy as long as PT or PTT is within therapeutic range of intended use of anticoagulants
Activated Partial Thromboplastin Time (aPTT)	≤1.5 X ULN unless subject is receiving anticoagulant therapy as long as PT or PTT is within therapeutic range of intended use of anticoagulants
a Creatinine clearance should be calculated per institutional standard.	

**Table 2. Adequate Organ Function Laboratory Values.**

12. Age ≥ 16 years.
13. ECOG performance status of 0 or 1.
14. Patients must consent and be willing to undergo tumor core needle biopsies at three timepoints (1. baseline, 2. prior to starting Cycle 3, and 3. at off-study). At least one tumor site must be amenable to biopsy in the judgment of the interventional radiologist.
15. Female subject of childbearing potential should have a negative urine or serum pregnancy within 72 hours prior to receiving the first dose of study medication. If the urine test is positive or cannot be confirmed as negative, a serum pregnancy test will be required.
16. Females of child bearing potential that are sexually active must agree to either practice 2 medically accepted highly effective methods of contraception at the same time or abstain from heterosexual intercourse from the time of signing the informed consent through 120 days after the last dose of study drug. See Appendix G for

protocol-approved highly effective methods of contraceptive combinations. Subjects of childbearing potential are those who have not been surgically sterilized or have not been free from menses for > 1 year.

- a. Negative test for pregnancy is required of females of child-bearing potential; A female of child bearing potential is any woman, regardless of sexual orientation or whether they have undergone tubal ligation, who meets the following criteria:
    1. has not undergone a hysterectomy or bilateral oophorectomy; or
    2. has not been naturally postmenopausal for at least 24 consecutive months (i.e., has had menses at any time in the preceding 24 consecutive months or 730 days).
  - b. Conception while on treatment must be avoided
17. Male subjects should agree to use an adequate method of contraception starting with the first dose of study therapy through 120 days after the last dose of study therapy. Prior history of vasectomy does NOT replace requirement for contraceptive use.
  18. Suitable venous access to allow for all study related blood sampling
  19. Ability to understand and willingness to sign a written informed consent document.
  20. For minors that are 16 to 18 years of age, assent **and** parental (or legally acceptable representative) written informed consent must be obtained.

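### Appendix G contradicts the eligibility criteria on how long contraception lasts and who is exempt from it, and the definition of childbearing potential used for pregnancy testing is not stated

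*Combined protocol and SAP*

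**What the plan says.** **Contraception: duration.** Section 5.1, criterion 16 (women), runs "through 120 days after the last dose of study drug". Criterion 17 (men) runs "starting with the first dose of study therapy through 120 days after the last dose of study therapy". Exclusion 15 in Section 5.2 uses the same 120-day limit for anyone expecting to conceive or father a child. The first paragraph of Appendix G also gives 120 days after the last dose. None of these carries an exception. The third paragraph of Appendix G, in a sentence on what subjects must do in order to take part, adds one: if new anticancer therapy is begun, the duty ends 30 days after treatment stops, if that comes sooner.

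**Contraception: who is exempt.** Criterion 16 says "Subjects of childbearing potential are those who have not been surgically sterilized or have not been free from menses for > 1 year". Appendix G lets a woman enrol without two methods if she is surgically sterilized, is aged 45 or over with more than a year without menses, or is not heterosexually active.

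**Pregnancy testing.** Part 16a opens with "Negative test for pregnancy is required of females of child-bearing potential" and continues "A female of child bearing potential is any woman, regardless of sexual orientation or whether they have undergone tubal ligation". Its two conditions are that she "has not undergone a hysterectomy or bilateral oophorectomy" or "has not been naturally postmenopausal for at least 24 consecutive months". Criterion 15 says "Female subject of childbearing potential should have a negative urine or serum pregnancy within 72 hours" of the first dose, without saying which definition applies. Section 12.1 requires testing of women of childbearing potential at screening and throughout the study, also without a definition. The synopsis repeats criteria 15, 16 and 16a.

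**The concern.** These are entry and reproductive-safety rules, and staff who follow one of them can breach another. A coordinator working from Appendix G could tell a subject who moves to another drug that contraception may stop at 30 days, when the criterion under which she enrolled requires 120. Section 8.8 ends treatment at progression, and Section 8.9 plans follow-up for subjects who start new therapy, so the clause covers a foreseeable way of leaving treatment. Appendix G itself warns that pembrolizumab may harm a fetus.

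The exemption matters because enrolment starts at age 16 and Section 7.1 notes that sarcoma patients are generally younger. Absence of menses in a woman under 45 is the case that the age floor addresses, and criterion 16 omits that floor.

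The two definitions inside criterion 16 are a lesser matter. Each may have its own purpose, but the protocol does not say so where the tests are ordered.

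**Working it through.** The plan states no figure on this point, so the check sets the texts side by side.

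**Duration**

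| Place | End of obligation | Exception |
|---|---|---|
| Criterion 16 (women) | 120 days after last dose | none |
| Criterion 17 (men) | 120 days after last dose | none |
| Exclusion 15 | 120 days after last dose | none |
| Appendix G, first paragraph | 120 days after last dose | none |
| Appendix G, third paragraph | 120 days, counted from completing the trial | 30 days after stopping if new therapy starts, when sooner |

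Counted from the same day, the gap is 120 − 30 = 90 days. It is smaller if new therapy starts later than day 30. With a start on day 60, for example, 120 − 60 = 60 days are lost.

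**Exemption and definition**

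The *or* in criteria 16 and 16a can be read in two ways. On the usual reading, either condition removes childbearing potential. On the literal reading, a woman who fails either condition is still included, so both are needed to remove it. Appendix G lists its conditions as plain alternatives. The examples are heterosexually active women, and tubal ligation is taken to be surgical sterilization.

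| Woman | Criterion 16, usual | Criterion 16, literal | Appendix G | 16a, usual |
|---|---|---|---|---|
| 40, no surgery, 14 months without menses | exempt | included | not exempt | included |
| 50, no surgery, 18 months | exempt | included | exempt | included |
| 30, tubal ligation, menstruating | exempt | included | exempt | included |
| 40, tubal ligation, 18 months | exempt | exempt | exempt | included |

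1. *Criterion 16 against Appendix G, usual reading.* They disagree on the 40-year-old with 14 months, and the cause is the age floor.
2. *Criterion 16 against Appendix G, literal reading.* That woman is now treated alike, but the 50-year-old with 18 months and the 30-year-old with tubal ligation are included by criterion 16 and exempt in Appendix G. The literal reading moves the disagreement to other women and does not remove it.
3. *Criterion 16 against 16a, usual reading.* All four examples differ, because 16a disregards tubal ligation and asks for 24 months instead of 1 year.

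**The case against.** The best reply is that criterion 16 refers to Appendix G only for approved contraceptive methods and sets both the population and the duration in its own text. The criterion would then prevail. This is right about the cross-reference, but it does not settle the matter, because Appendix G is not confined to methods. It says who may be enrolled and what subjects must do to participate, and its two statements on duration disagree with each other.

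A second reply is that 16a opens with the pregnancy-test rule, so a stricter net for testing beside a different one for contraception is deliberate. That is probably so, and it reduces this part to a request to state the scope of 16a.

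A third is that progression does not always end treatment. Section 11.0 lets some subjects continue after RECIST progression, and Sections 8.1 and 8.2 allow pembrolizumab to be re-introduced after progression on axitinib alone. Criterion 16b and exclusion 15 also still bar conception. All of this stands. It limits how often the 30-day clause would apply, but the clause still contradicts the criteria.

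A reader might also infer that criteria 16 and 16a conflict however they are read. The fourth woman in the table suggests this, but only if tubal ligation counts as surgical sterilization. If the hysterectomy and oophorectomy wording of 16a is taken to explain that phrase, both texts include her on the literal reading.

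**Conclusion.** The point holds as an inconsistency of wording in entry and safety rules, and it should be corrected. The duration conflict rests on no interpretation: four places give an unconditional 120 days and one clause allows 30, a gap of up to 90 days. The exemption conflict is the age-45 floor on the usual reading of *or*; on the literal reading the two texts disagree about other women. The 16 against 16a difference is a matter of unstated scope.

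Three larger conclusions may tempt a reader and are not supported.

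- *That the size can be given in women affected.* The documents give no numbers by sterilization or menopausal status, and counts of hypothetical profiles depend on which profiles are chosen.
- *That the 90 days measure fetal risk.* Against the 26-day pembrolizumab half-life in Section 9.2.3, 90/26 is about 3.5 half-lives. That is relevant only to someone who stops while still receiving pembrolizumab. After long axitinib monotherapy it means little, since Section 9.1.3 gives axitinib a half-life of 2.5 to 6.1 hours. The documents link no drug level to fetal harm.
- *That trial results are at stake.* No efficacy analysis, sample size or error rate depends on these rules.

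**What to change.** 1. Delete the 30-day new-therapy clause from the third paragraph of Appendix G. In the same sentence, count the 120 days from the last dose, so that one rule applies throughout.
2. State in criterion 15 and Section 12.1 that 16a defines who is pregnancy-tested.
3. Use one contraception exemption in criterion 16, its synopsis copy and Appendix G. Introduce it with *exempt if any one of the following applies*, so that *or* has one meaning, and keep the age-45 floor on the 1-year rule.
4. Do not extend 16a to contraception. It has no age floor, and it would require sexually active women with tubal ligation to use two methods or abstain in order to enrol, which is a substantive eligibility change.

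The cost is protocol wording and a check that the consent form, which was not available here, matches. Some women under 45 without menses for more than a year would have to use contraception, and some subjects would continue it for up to 90 days longer. The documents do not allow either group to be counted.

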## 5.2 Exclusion Criteria

1. Prior therapy with axitinib. Patients are permitted to have received prior tyrosine kinase inhibitor (TKI) therapy including imatinib, sunitinib, pazopanib, or similar. Patients may have received prior PD-1 or PD-L1 directed therapy.
2. Hypersensitivity to axitinib, pembrolizumab or any of its excipients.
3. Patients may not be receiving any other investigational agents (within 4 weeks prior to Cycle 1, day 1).
4. Prior anti-cancer monoclonal antibody (mAb) within 4 weeks prior to Cycle 1, day 1 or has not recovered (i.e.,  $\leq$  Grade 1 or at baseline) from adverse events due to agents administered more than 4 weeks earlier.
5. Patient has had prior chemotherapy, targeted small molecule therapy, or radiation therapy within 2 weeks prior to Cycle 1, Day 1 or has not recovered (i.e.,  $\leq$  Grade 1 or at baseline) from adverse events due to agents administered more than 4 weeks earlier. Subjects with  $\leq$  Grade 2 neuropathy are an exception to this criterion and may qualify for the study. Note: If subject received major surgery, they must have recovered adequately from the toxicity and/or complications from the intervention prior to starting therapy.
6. Additional known malignancy that is progressing or requires active treatment. Exceptions include basal cell carcinoma of the skin, or squamous cell carcinoma of the skin that has undergone potentially curative therapy, or in situ cervical cancer.
7. Patients with end-organ dysfunction as defined in inclusion criterion (i.e. #11 above).
8. Patients with bone-only lesions.
9. Patients with underlying immune deficiency, chronic infections including HIV, hepatitis, or tuberculosis (TB) or autoimmune disease.

10. Patients with underlying hematologic issues including bleeding diathesis, known previous GI bleeding requiring intervention within the past 6 months, active pulmonary emboli or DVT that are not stable on anticoagulation regimen.
11. Has known history of, or any evidence of active, non-infectious pneumonitis.
12. Has known active central nervous system (CNS) metastases and/or carcinomatous meningitis or leptomenigeal disease. Subjects with previously treated brain metastases may participate provided they are stable (without evidence of progression by imaging for at least four weeks prior to the first dose of trial treatment and any neurologic symptoms have returned to baseline), have no evidence of new or enlarging brain metastases, and are not using steroids for at least 7 days prior to trial treatment. This exception does not include carcinomatous meningitis which is excluded regardless of clinical stability.
13. Concomitant (or receipt of) treatment with medications that may affect the metabolism of pembrolizumab and/or axitinib within 7 days prior to Cycle 1, day 1 of axitinib.
14. Has received a live vaccine within 30 days of planned start of study therapy. Note: Seasonal influenza vaccines for injection are generally inactivated flu vaccines and are allowed; however intranasal influenza vaccines (e.g., Flu-Mist®) are live attenuated vaccines, and are not allowed.
15. Is pregnant or breastfeeding, or expecting to conceive or father children within the projected duration of the trial, starting with the pre-screening or screening visit through 120 days after the last dose of trial treatment.
16. Any uncontrolled, intercurrent illness including but not limited to ongoing or active infection, symptomatic congestive heart failure, unstable angina pectoris, cardiac arrhythmia
17. Prolonged QTc interval on Screening EKG >475 ms.
18. Ejection Fraction <40% by 2D ECHO at Screening.
19. Any serious medical or psychiatric illness/condition including substance use disorders likely in the judgment of the Investigator(s) to interfere or limit compliance with study requirements/treatment.
20. Has active autoimmune disease that has required systemic treatment in the past 2 years (i.e. with use of disease modifying agents, corticosteroids or immunosuppressive drugs). Replacement therapy (eg., thyroxine, insulin, or physiologic corticosteroid replacement therapy for adrenal or pituitary insufficiency, etc.) is not considered a form of systemic treatment.

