
Exclusion Criteria
	
 
1. Prior therapy with axitinib. Patients are permitted to have received prior tyrosine kinase inhibitor (TKI) therapy including imatinib, sunitinib, pazopanib, or similar. Patients may not have received prior PD-1 or PD-L1 directed therapy.
 
2. Hypersensitivity to axitinib, pembrolizumab or any of its excipients.
 
3. Patients may not be receiving any other investigational agents (within 4 weeks prior to Cycle 1, day 1).
 
4. Prior anti-cancer monoclonal antibody (mAb) within 4 weeks prior to Cycle 1, day 1 or has not recovered (i.e., <math>\leq</math> Grade 1 or at baseline) from adverse events due to agents administered more than 4 weeks earlier.
 
5. Patient has had prior chemotherapy, targeted small molecule therapy, or radiation therapy within 2 weeks prior to Cycle 1, Day 1 or has not recovered (i.e., <math>\leq</math> Grade 1 or at baseline) from adverse events due to agents administered more than 4 weeks earlier. Subjects with Grade 2 neuropathy are an exception to this criterion and may qualify for the study. Note
 

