**Table 10. Dose Titration of Axitinib**

a Dosing modifications based only on the following grade 2 toxicities: oral mucositis, diarrhea, hand-foot syndrome, fatigue. Dose modifications for other drug-related AEs as per table below and as per study principal investigator. CTC v4 definitions of grade 2 toxicities:

Oral mucositis: Moderate pain; not interfering with oral intake; modified diet indicated

Diarrhea: Increase of 4 - 6 stools per day over baseline

HFS: Skin changes (e.g., peeling, blisters, bleeding, edema, or hyperkeratosis) with pain; limiting instrumental ADL

Fatigue: Fatigue not relieved by rest; limiting instrumental ADL

b After dose reduction, re-escalation as tolerated may be considered per provider discretion

Toxicity	Grade:	Treatment	Dose reduction
Hypertension/ Hypertensive crisis  (Defined as $\geq$ 150/100 or symptoms such as headache, chest pressure, blurry vision)	2	Add appropriate anti-hypertensive medications	No dose reduction required
	3	Add appropriate anti-hypertensive medications	If persistent despite 3 or more medications and associated with persistent symptoms, dose reduce one level
	4	Discontinue axitinib	Discontinue axitinib
Thrombotic events (arterial)	2-4	Discontinue axitinib	Discontinue axitinib
Thrombotic events (venous) – uncomplicated DVT/PE	3	Provide anticoagulation	No dose adjustment required
Other venous thromboembolic disease (ie retinal vein occlusion)	3	Consider discontinuation of axitinib	Consider discontinuation of axitinib
Hemorrhage	2	Hold axitinib until resolution to $\leq$ grade 1	Dose reduce one dose level

	3	Hold axitinib until resolution to $\leq$ grade 1	Dose reduce one dose level. Discontinue if recurs with restarting medication.
	4	Discontinue axitinib.	Discontinue axitinib.
Thyroid dysfunction	2	Treat with replacement/suppression	No dose change
	3	Treat with replacement/suppression. Hold axitinib until resolution to $\leq$ grade 1. *refer to pembrolizumab dose modifications for additional treatment	Dose reduce one dose level
	4	Discontinue axitinib	Discontinue axitinib
Reversible posterior Leukoencephalopathy Syndrome	2-4	Discontinue axitinib	Discontinue axitinib

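### Exclusion 5 leaves a window of 15 to 28 days before Day 1 in which recovery from prior-treatment toxicity is not required

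*Combined protocol and SAP*

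**What the plan says.** Criterion 5 in Section 5.2 has two limbs. The first is a washout for chemotherapy, targeted small-molecule drugs and radiation: "radiation therapy within 2 weeks prior to Cycle 1, Day 1 or has not recovered". The second requires recovery to Grade 1 or less, or baseline, but only "from adverse events due to agents administered more than 4 weeks earlier". The Synopsis pairs the same limbs: "targeted small molecule therapy, or radiation therapy within 2 weeks prior to Cycle 1, Day 1 or has not recovered", followed by the same 4-week look-back.

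Criterion 4 uses the same recovery clause with a longer washout: "Prior anti-cancer monoclonal antibody (mAb) within 4 weeks prior to Cycle 1, day 1 or has not recovered". Criterion 3 also uses 4 weeks: "Patients may not be receiving any other investigational agents (within 4 weeks prior to Cycle 1, day 1".

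Criterion 5 names one exception to recovery: "Grade 2 neuropathy are an exception to this criterion and may qualify for the study". Its note on major surgery asks for adequate recovery before therapy starts and sets no look-back.

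On the dosing side, footnote a to Table 10 (Section 10.2) reads "Dosing modifications based only on the following grade 2 toxicities: oral mucositis, diarrhea, hand-foot syndrome, fatigue".

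**The concern.** A recovery rule is there to stop residual toxicity from earlier treatment being carried into the study. Here the patients nearest their last dose, once past the washout, are the only ones it does not reach. The effect is inverted: the same unresolved toxicity excludes a patient at 5 weeks and admits one at 3 weeks. No rationale is given.

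Patient safety is one thing at stake. The other is how axitinib titration is read. Section 10.2 allows dose reduction at any time for Grade 2 or greater toxicity. It makes escalation on Cycle 2 Day 1 conditional on there being none. The four toxicities in the Table 10 footnote are ones that prior treatment may also leave behind, and Section 5.2 expressly permits prior tyrosine kinase inhibitors. If such a toxicity is present at entry, the titration record reflects it along with tolerance of the study drug.

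**Working it through.** No power or sample-size figure is involved. The check is interval logic on criterion 5, followed by a search of the other criteria for one that closes the gap.

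**Inputs** (Section 5.2, criterion 5; same in the Synopsis)
- Washout limb: 2 weeks = 14 days or less before Cycle 1 Day 1.
- Recovery limb: more than 4 weeks = more than 28 days before.

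**Coverage by days from last dose to Day 1**

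| Days before Day 1 | Washout limb | Recovery limb | Unrecovered patient |
|---|---|---|---|
| 0-14 | applies | does not apply | excluded |
| 15-28 | does not apply | does not apply | not excluded by criterion 5 |
| 29 or more | does not apply | applies | excluded |

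Width of the uncovered interval: 28 - 15 + 1 = 14 days.

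**Comparison with criterion 4.** Its washout is 4 weeks (28 days) and its recovery limb starts beyond 28 days, so the limbs meet. It cannot fill the gap in criterion 5, because its recovery clause has the same look-back. Monoclonal antibodies (criterion 4) and investigational agents (criterion 3) therefore stay outside the gap.

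**Does another criterion close it?**
- Criterion 7, "Patients with end-organ dysfunction as defined in inclusion criterion (i.e. #11 above", points to Table 2, which covers blood counts and renal, hepatic and coagulation values. It blocks many laboratory toxicities but has no entry for mucositis, diarrhea, hand-foot syndrome or fatigue.
- ECOG 0-1 overlaps in part. Table 10 defines Grade 2 fatigue and hand-foot syndrome by limits on instrumental daily activities, while Appendix C describes ECOG 1 as still able to do light work. Grade 2 mucositis, defined there as moderate pain that does not interfere with oral intake, is compatible with ECOG 0 or 1.
- Criteria 11 and 16-19 cover pneumonitis, uncontrolled illness, QTc, ejection fraction and conditions that the investigator judges likely to interfere. None sets a grade for these four toxicities.

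**Route to the titration data.** Tables 4 and 11 adjust for liver tests that are abnormal at entry. Table 10 has no matching rule for the four toxicities. Its diarrhea definition counts stools over baseline, but it does not say whether a toxic pre-study state is that baseline.

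**How long must carry-over last to block the first escalation?** Cycle 1 is 49 days (Section 7.2), so Cycle 2 Day 1 falls 49 days after Cycle 1 Day 1. For a last dose 15 to 28 days before Day 1, the toxicity must persist for 15 + 49 = 64 to 28 + 49 = 77 days after that dose. Dose reduction during cycle 1 needs no such persistence.

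**The case against.** The strongest reply accepts the literal gap and disputes its consequences. Much of that reply stands.

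- **Other screens.** Table 2, ECOG 0-1, criteria 11 and 16-19 and investigator judgment would stop many severe toxicities. A reader might infer that any Grade 2 to Grade 4 toxicity can enter. The documents do not support that; the exposure is mainly to non-laboratory toxicity compatible with good performance status.
- **Misattribution.** A reader might infer that carried-over toxicity simply becomes a study-drug event or a DLT. Section 15.4 limits adverse events to those that begin or worsen after treatment starts, Section 12.1 has pretreatment conditions documented and reassessed, and Section 7.2 requires the investigator to judge a DLT at least possibly related. Stable carry-over is therefore not a DLT. Worsening of it in cycle 1 could still be attributed to study drug.
- **The lead-in.** It is tempting to size the problem by its effect on the five-patient safety decision. Section 1.5 reports that the first 30 patients are accrued, so no amendment can alter that stage, and nothing shows that a lead-in patient fell in the window.
- **Who remains.** The expansion is up to 10 patients with ASPS, who may enroll untreated, so few may be affected.
- **Escalation.** The 64 to 77 days of persistence make a blocked first escalation less likely than an early reduction.
- **Neuropathy wording.** The Synopsis gives Grade 2 where Section 5.2 gives Grade 2 or less. Nearby Synopsis text has also lost characters, so this is probably a dropped symbol and is not relied on.

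None of this supplies a recovery requirement for days 15 to 28.

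**Conclusion.** The gap is real on the current text of both Section 5.2 and the Synopsis: 14 days, affecting chemotherapy, targeted small molecules and radiation only. It admits unresolved Grade 2 or higher mucositis, diarrhea or hand-foot syndrome, subject to the partial screens above. The likely effects are axitinib reduction, sometimes a barred escalation, and possible attribution of worsening toxicity to study drug in cycle 1.

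The number of patients affected is not stated and cannot be estimated from the documents. What remains is the effect on expansion enrollment and on the interpretation of patients already enrolled.

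The conclusion assumes that time is counted from the last dose. The text does not say so. For a long continuous course, someone might count from earlier doses and treat the patient as covered. That ambiguity is a further reason to reword. The matching limbs of criterion 4, the open-ended surgery note and the single named exception suggest that a general recovery rule was meant, but that is inference.

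**What to change.** Reconcile the washout and recovery limbs of criterion 5 in Section 5.2, the Synopsis and the eligibility checklist, so that no interval since last therapy is left without a recovery requirement. The interval and the wording are the sponsor's clinical decision. State whether time runs from the last dose.

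For patients already enrolled, compare last-dose dates with the baseline toxicity grades recorded as pretreatment events. Identify anyone who entered from the 15-to-28-day window with unresolved toxicity, so that their titration and cycle 1 toxicity can be read accordingly.

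The cost is a short wording amendment, a checklist update and a limited data check. The downside is that a few patients may start later while toxicity resolves.
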